6.5.3. Up-Titration

Any participant who does not reach the target serum phosphate level of > 5.5 mg/dL at any time during Cycle 1, are compliant with taking study drug and do not experience an ongoing Grade 2 or higher treatment-related AEs will increase the daily dose to 18 mg starting from Cycle 2 Day 1.

Participants who are titrated up to 18 mg QD will begin the next cycle at the new dose level and must agree to all Cycle 1 assessments. Up-titration may occur no earlier than Cycle 2 Day 1 so that subjects are observed for phosphate level and AEs for at least 1 cycle.

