2.2.2. Justification for Dose and Regimen

Pemigatinib will be administered at 13.5 mg QD, continuously, during a cycle. Each cycle is 3 weeks. This dose and dosing schedule was selected based on emerging clinical and safety data from the INCB 54828-101 study, where the continuous dosing regimen has been tested in 8 and 16 participants at 9 mg and 13.5 mg QD continuous administration, respectively. In Study INCB 54828-101, the emerging safety data demonstrated that tolerability of the continuous dosing regimen of pemigatinib was comparable to that of intermittent dosing.

The hypothesis with a targeted therapy is that continued inhibition of the aberrant receptor may increase the potential for benefit from the treatment. Therefore, administering pemigatinib continuously will allow that consistent inhibition of the aberrant FGFR receptor in this population. Continuous dosing would still allow for dose holds for safety reasons with criteria and procedures for dose interruptions and adjustments clearly outlined in the Protocol.

Hyperphosphatemia is an expected on-target pharmacological effect of FGFR inhibition. The incidence of hyperphosphatemia, defined as any postbaseline phosphate level exceeding 5.5 mg/dL, has been observed in the majority of participants treated with pemigatinib (refer to the [IB](#) for complete data). Some participants do not achieve hyperphosphatemia, and it is estimated that pharmacological concentration of pemigatinib in these participants is lower (see [Figure 2](#)). Therefore, up-titration of pemigatinib will be used to increase the exposure of pemigatinib in participants who do not achieve hyperphosphatemia when treated with 13.5 mg QD. The goal is to increase the serum concentration of pemigatinib.

Any participant who does not reach the target serum phosphate level of > 5.5 mg/dL at any time during Cycle 1, and who is compliant with taking study drug and does not experience an ongoing Grade 2 or higher treatment-related AEs, will increase the daily dose to 18 mg starting at Cycle 2 Day 1.

Dose modifications for tolerability issues are noted in Section 6.5.

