6.5. Dose Modifications

Individual decision regarding dose modifications of pemigatinib should be made using clinical judgement and in consultation with the sponsor's medical monitor, taking into account relatedness of the AE to the study treatment and the participant's underlying condition. Adverse events that have a clear alternative explanation or transient (≤ 72 hours) abnormal laboratory values without associated clinically significant signs or symptoms, may be exempt from dose-reduction rules.

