6.5.1. Criteria and Procedures for Dose Interruptions and Adjustments of Study Drug

Safety concerns should be discussed with the sponsor immediately upon occurrence or awareness to determine if the participant should continue or discontinue study treatment.

Treatment with pemigatinib may be delayed up to 2 weeks (14 days) to allow for resolution of toxicity. Participants may resume treatment if no medical condition or other circumstance exists that, in the opinion of the investigator, would make the participant unsuitable for further participation in the study. The treating investigator should contact the sponsor to discuss the case of any participant whose treatment has been delayed for more than 14 days before restarting treatment with pemigatinib. Refer to [Table 10](#) for guidelines.

Table 10: Guidelines for Interruption and Restarting of Study Drug

ADVERSE EVENT	ACTION TAKEN
Chemistry	

 AST and/or ALT is $> 5.0 \times$ ULN. Note: In participants with liver metastasis-related elevations at baseline, contact sponsor to discuss clinical management and possible dose reductions. 	
Step 1: Interrupt pemigatinib up to 2 weeks (14 days) until the toxicity has resolved to \leq Grade 1 except by approval of the medical monitor.
 
Step 2: Restart pemigatinib at same dose. If assessed as related to pemigatinib, restart pemigatinib at next lower dose; monitor as clinically indicated.

Other toxicities	

 Any Grade 1 or Grade 2 toxicity. 	Continue pemigatinib treatment and treat the toxicity; monitor as clinically indicated.

 Any Grade 3 toxicity, if clinically significant and not manageable by supportive care. 	
Step 1: Interrupt pemigatinib up to 2 weeks (14 days), until toxicity resolves to \leq Grade 1.
 
Step 2: Restart pemigatinib at same dose. If assessed as related to pemigatinib, restart pemigatinib at next lower dose; monitor as clinically indicated.

 Any recurrent Grade 3 toxicity after 2 dose reductions. 	Discontinue pemigatinib administration and follow-up per Protocol (exceptions require approval of sponsor).

 Any other Grade 4 toxicity. 	Discontinue pemigatinib administration and follow-up per Protocol.

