The sponsor recommends a maximum of 2 level dose reductions: participants treated at 13.5 mg can decrease to 9 mg, and if additional dose reduction is required, participants can decrease to 4.5 mg. Dose reductions below 4.5 mg are not allowed. The frequency of dosing (ie, QD) as well as the schedule (ie, continuous dosing) remain the same.

For participants who are up-titrated from 13.5 mg to 18 mg, a maximum of 2 dose level reductions is also recommended. The 18-mg dose can be decreased to 13.5 mg, and if additional dose reduction is required, participants can decrease to 9 mg. Dose reductions below 9 mg are not allowed.

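### The up-titration rule in 6.5.3, followed as written, can raise to 18 mg a participant whose dose Table 10 has just cut to 9 mg for a related toxicity

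*Protocol*

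**What the plan says.** Section 6.5.3 sets three conditions for 18 mg from Cycle 2 Day 1: serum phosphate not above 5.5 mg/dL at any time in Cycle 1, compliance with study drug, and no Grade 2 or higher related event still present. The last condition and the instruction read "do not experience an ongoing Grade 2 or higher treatment-related AEs will increase the daily dose to 18 mg". Section 2.2.2 repeats the rule and is equally directive: such a participant "will increase the daily dose to 18 mg starting at Cycle 2 Day 1".

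The rationale in 2.2.2 describes the intended group as "participants who do not achieve hyperphosphatemia when treated with 13.5 mg QD".

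Table 10 in section 6.5.1 covers a Grade 3 toxicity that is clinically significant and cannot be managed by supportive care. Drug is held for up to 14 days until the toxicity is Grade 1 or lower. Then: "If assessed as related to pemigatinib, restart pemigatinib at next lower dose; monitor as clinically indicated". The row for AST or ALT above 5 times ULN works the same way, unless the medical monitor approves otherwise. For the size of the step, 6.5.1 states that "participants treated at 13.5 mg can decrease to 9 mg", with 4.5 mg as a second step.

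Reduction steps from 18 mg are also in 6.5.1, for one route only: "For participants who are up-titrated from 13.5 mg to 18 mg, a maximum of 2 dose level reductions is also recommended". For that group, "Dose reductions below 9 mg are not allowed".

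**The concern.** Two dosing rules can apply to the same participant at the same time and give opposite answers. Table 10 restarts at 9 mg once the toxicity has settled. Section 6.5.3 stops an increase only while a toxicity is unsettled. A participant who has recovered enough to restart at the lower dose has therefore also recovered enough to meet the adverse-event condition for the higher one. No text says which rule prevails, and there is no rule on raising a dose after a reduction.

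The hold may also help to satisfy the phosphate condition. Section 2.2.2 links absent hyperphosphatemia to lower drug concentration, and a hold or reduction lowers exposure. Low phosphate in such a participant may reflect the missed drug rather than under-exposure at 13.5 mg.

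What is at stake is the safety of an individual participant: an increase above the dose on which a significant related toxicity has just occurred.

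**Working it through.** The protocol states no figure to reproduce. The check is whether a participant managed under Table 10 can meet every condition of 6.5.3, and what dose would follow.

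**Inputs.** Starting dose 13.5 mg QD (6.1); 21-day cycles, so Cycle 2 Day 1 is nominally Day 22 (section 1, 2.2.2); next lower dose 9 mg (6.5.1); up-titrated dose 18 mg (6.5.3); maximum hold 14 days (Table 10). Compliance is calculated from tablet counts (6.4), and nothing there treats a hold or reduction directed by the protocol as noncompliance.

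**Case 1: dose already reduced.** Related Grade 3 event on Day 8, held Days 8 to 14, restarted at 9 mg on Day 15, phosphate never above 5.5 mg/dL, drug taken as directed.

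| Condition in 6.5.3 | Status on Day 22 |
|---|---|
| Phosphate never > 5.5 mg/dL in Cycle 1 | met |
| Compliant | met |
| No ongoing Grade 2 or higher related event | met (Grade 1 or lower since Day 15) |
| Still assigned 13.5 mg | not asked |

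The rule gives 18 mg.

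- Relative to the current dose: 18 / 9 = 2.0
- Relative to the dose at the event: 18 / 13.5 = 1.33
- Cycle 2 total at 18 mg: 21 × 18 = 378 mg
- Cycle 2 total at 9 mg: 21 × 9 = 189 mg

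**Case 2: reduction due on the same day.** Related Grade 3 event on Day 8, held Days 8 to 21, at Grade 1 or lower by Day 22. Table 10 gives 9 mg for Day 22 and 6.5.3 gives 18 mg for Day 22.

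**Drug actually received in Cycle 1.** Planned: 21 × 13.5 = 283.5 mg.

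- Case 1: 7 × 13.5 + 7 × 9 = 94.5 + 63 = 157.5 mg; 157.5 / 283.5 = 56%
- Case 2: 7 × 13.5 = 94.5 mg; 94.5 / 283.5 = 33%

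Table 4 schedules Cycle 1 chemistry on Days 1, 8 and 15. On nominal days in case 1, the Day 15 sample follows a week off drug, so Day 8 is the only on-treatment sample reflecting 13.5 mg. Table 6 shows hyperphosphatemia on continuous dosing in 4 of 8 participants (50%) at 9 mg and 14 of 16 (87.5%) at 13.5 mg. These are small numbers covering any time on study, but the direction fits the rationale in 2.2.2.

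**Steps down from 18 mg.** Section 6.5.1 defines them only for a move from 13.5 to 18 mg, so none are defined after a move from 9 to 18 mg. If they were applied anyway, the floor would be 9 mg, and the 4.5 mg level that was open after the first reduction would be closed.

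**Scale.** The number affected cannot be derived from the protocol. As an outer group only: (16 − 14) / 16 = 12.5% on 13.5 mg continuous had no reported hyperphosphatemia (exact 95% CI 1.6% to 38.3%). Applied to 50 participants, that is about 6 (0.8 to 19) to whom up-titration might apply at all. Because Table 6 covers any time on study, the share without hyperphosphatemia in Cycle 1 alone may be higher. Nearly all of these would be up-titrated properly; the affected participants are a small subset.

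**The case against.** The strongest reply is that 6.5.3 should not be read alone. It sits under 6.5, which opens with "Individual decision regarding dose modifications of pemigatinib should be made using clinical judgement and in consultation with the" sponsor's medical monitor, and a lead clause governs its subsections. The rationale and the reduction steps mention up-titration only from 13.5 mg. Section 6.5.3 adds that up-titration may come no earlier than Cycle 2 Day 1, so that phosphate and adverse events are watched for at least one cycle, and it requires the Cycle 1 assessments to be repeated at 18 mg. Section 8.3.6 calls for more frequent phosphate testing after up-titration and for acceptable laboratory results before each cycle. Table 3 marks up-titration as something to assess, 6.5.1 asks that safety concerns go to the sponsor at once, and Table 10 stops drug for Grade 4 toxicity. Several uncommon events must coincide, and the sponsor and investigator would have to double a dose they had just cut. The phase 1/2 study reached no MTD and had no monotherapy DLTs, and 6.6.1 calls 20 mg QD tolerable.

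Most of this stands as evidence that the result is unintended and improbable. It does not remove the conflict. The judgement clause is general, whereas the up-titration sentence is specific and says the dose will increase. The one-cycle sentence fixes the earliest date, not who qualifies. Repeat assessments and closer phosphate testing follow the increase and do not prevent it. The 13.5 mg wording in 2.2.2 is rationale, and a participant who started on 13.5 mg and was then reduced still fits it. The tolerability statements rest on 6 participants at 20 mg continuous (Table 6) and do not address someone who has just needed a reduction from 13.5 mg.

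Two limits are accepted: the loss of the 4.5 mg level depends on applying steps not written for this route, and the Table 6 figures do not measure the problem.

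**Conclusion.** The point holds. Followed as written, 6.5.3 and its copy in 2.2.2 give 18 mg to a compliant participant with low Cycle 1 phosphate whose related toxicity has resolved, even where Table 10 has set or requires 9 mg. The increase is 2.0 times the current dose and 1.33 times the dose at which the toxicity occurred.

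This rests on two readings: that a hold or reduction directed by the protocol does not count as noncompliance, and that the general clause in 6.5 does not override the specific instruction. If the second is read the other way, the outcome depends on case-by-case judgement and the two rules still disagree on paper.

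The case should be rare, no count is claimed, and neither the sample size nor the primary analysis is affected. It is a participant-safety clarification that should be made at the next amendment.

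**What to change.** In 6.5.3 and the matching sentence of 2.2.2, add that up-titration applies only to participants who are still assigned 13.5 mg QD at the end of Cycle 1 and for whom no dose reduction for a treatment-related adverse event has been made or is required under Table 10. Whether an interruption without a reduction should also bar the increase is for the sponsor to decide.

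The cost is one clause in each of two sentences. It adds no visits, procedures or participants and leaves the sample size and analysis unchanged. A very small number of participants would stay at 9 mg instead of moving to 18 mg, which is what the dose rationale and the reduction steps already imply.

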6.5.4. Criteria for Permanent Discontinuation of Study Drug

The occurrence of unacceptable toxicity not caused by the underlying disease will require that the study drug be permanently discontinued. Unacceptable toxicity is defined as follows:

- Occurrence of an AE that is related to study drug that, in the judgment of the investigator or the sponsor's medical monitor, compromises the participant's ability to continue study-specific procedures or is considered to not be in the participant's best interest.
- An AE requiring more than 2 dose reductions.
- Persistent AE requiring a delay of therapy for more than 2 weeks (14 days) unless a greater delay has been approved by the sponsor.
- Increase in QT/QTc to > 500 milliseconds or to > 60 milliseconds over baseline. In case of a QTc > 500 milliseconds, the participant must be hospitalized and continuous ECG monitoring must be set up until the measure of the QTc interval decreases below 500 milliseconds and is acceptable in the opinion of the local cardiologist.

See Section [7](#) for discontinuation procedures.

6.6. Concomitant Medications and Procedures

All concomitant medications and treatments (including over-the-counter or prescription medicines, vitamins, vaccines, and/or herbal supplements) must be recorded in the eCRF. Any prior medication received up to 35 days before the first dose of study treatment and 30 to 35 days after the last dose of study treatment, or until the participant begins a new anticancer therapy, whichever occurs first, will be recorded in the eCRF. Any addition, deletion, or change in the dose of these medications will also be recorded. Concomitant medications administered after 30-35 days after the last dose of study treatment should be recorded for SAEs as defined in Section [9.2](#). Concomitant treatments/procedures that are required to manage a participant's medical condition during the study will also be recorded in the eCRF. The medical monitor should be contacted if there are any questions regarding concomitant or prior therapy.

6.6.1. Restricted Medications and Procedures

Pemigatinib is predominantly metabolized by CYP3A4. There is an expected 50% increase in exposure in participants who concomitantly use CYP3A4 moderate inhibitors. However, as doses above the recommended Phase 2 dose of 13.5 mg QD have been tested (20 mg QD is tolerable), there is a sufficient safety margin. Therefore, the use of moderate CYP3A4 inhibitors is not prohibited but should involve careful monitoring, especially in relation to safety, while moderate CYP3A4 inducers and potent CYP3A4 inhibitors and inducers are prohibited (see [Appendix D](#)).

Careful monitoring is required when pemigatinib is concomitantly administered with organic cation transporter 2 substrates such as dofetilide and metformin.

Calcium-based phosphate binding medications should not be used due to a concern for soft tissue mineralization.

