2.3.1. Study INCB 54828-101

Of the 150 participants with advanced malignancies who have been enrolled in Study INCB 54828-101 as of the data cutoff date, 43 participants have been administered pemigatinib in Part 1 (monotherapy dose escalation), 63 participants in Part 2 (monotherapy dose expansion), and 44 participants in Part 3 (pemigatinib combined with gemcitabine and cisplatin [8 participants], docetaxel [7 participants], pembrolizumab [23 participants], and trastuzumab [6 participants]).

Dose limiting toxicities informed dose escalation procedures during Part 1 of the study. Among participants in Part 1, 28 received pemigatinib at doses of 1 to 20 mg QD on a 2-weeks-on/1-week-off therapy schedule (ie, interval dose regimen), and 15 participants received pemigatinib at doses of 9, 13.5, or 20 mg QD on a continuous schedule (ie, continuous dose regimen). There were no DLTs for the monotherapy dose regimens, and the monotherapy MTD was not reached. The recommended Part 2 dose for pemigatinib was determined to be 13.5 mg based on PD and clinical effect, and the recommended Phase 2 dose regimens for pemigatinib based on safety and pharmacokinetic data and preliminary signals of clinical benefit were 13.5 mg QD following the interval schedule and 13.5 mg QD following the continuous schedule.

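### The safety margin that Section 6.6.1 gives for moderate CYP3A4 inhibitors holds up to about 13.5 mg of pemigatinib but not at the 18 mg up-titration dose

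*Protocol*

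**What the plan says.** Section 6.6.1 gives the size of the interaction: "There is an expected 50% increase in exposure in participants who concomitantly use CYP3A4 moderate inhibitors". It then states the margin: doses above 13.5 mg QD "have been tested (20 mg QD is tolerable), there is a sufficient safety margin". From this it concludes that "the use of moderate CYP3A4 inhibitors is not prohibited but should involve careful monitoring". The permission names no pemigatinib dose.

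Section 6.5.3 covers participants whose serum phosphate never exceeds 5.5 mg/dL in Cycle 1, who are compliant, and who have no ongoing treatment-related AE of Grade 2 or higher. Such a participant "will increase the daily dose to 18 mg starting from Cycle 2 Day 1". Up-titrated participants "will begin the next cycle at the new dose level and must agree to all Cycle 1 assessments". Concomitant inhibitors are not among the conditions. Section 2.2.2 gives the reason for up-titration: when phosphate does not rise, "it is estimated that pharmacological concentration of pemigatinib in these participants is lower".

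On doses already tested, Section 2.3.1 reports that in Part 1 of the earlier study "15 participants received pemigatinib at doses of 9, 13.5, or 20 mg QD on a continuous schedule". Table 6 shows 6 participants at 20 mg continuous and 6 at 20 mg on the interval schedule. Section 2.3.1 adds: "There were no DLTs for the monotherapy dose regimens, and the monotherapy MTD was not reached".

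Exclusion 21 (Section 5.2) and Section 6.6.2 bar potent inhibitors, potent inducers and moderate inducers. Moderate inhibitors are barred in neither place. Section 8.4 says that pharmacokinetics are not evaluated.

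**The concern.** The margin compares one dose, raised by 50%, with one tolerated dose. The permission drawn from it applies to every dose in the study, including 18 mg. A participant on 18 mg who is prescribed fluconazole, diltiazem, aprepitant or ciprofloxacin (all moderate inhibitors in Appendix D) stays on 18 mg, and the stated reason for allowing this was not worked out for that dose. A participant may also already be taking such a drug when up-titration is decided, since entry does not exclude it.

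Exposure is not measured, so an excess would show only through phosphate or adverse events. The phosphate schedule is unclear at this very dose. Section 8.3.6 requires more frequent testing for participants who are up-titrated and refers to Table 4. The Table 4 note adds a Day 8 test in later cycles only after hyperphosphatemia in Cycle 1, and Section 6.5.3 does not up-titrate those participants.

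**Working it through.** **Inputs.** Inhibitor effect +50% (6.6.1); reference dose 20 mg QD (6.6.1, Table 6); study doses 4.5, 9, 13.5 and 18 mg (Table 9).

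**Formula.** Dose-equivalent with inhibitor = dose x 1.5. This is the dose that alone would give the same exposure if exposure is proportional to dose. The protocol does not state proportionality, so it is an assumption.

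**The protocol's own margin.** 13.5 x 1.5 = 20.25 mg, against 20 mg: 1.25% over, so the reasoning reproduces at 13.5 mg.

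**All doses.**

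| Dose (mg) | With inhibitor (mg-equivalent) | Against 20 mg |
|---|---|---|
| 4.5 | 6.75 | 66% below |
| 9 | 13.5 | 32.5% below |
| 13.5 | 20.25 | 1.25% above |
| 18 | 27.0 | 35% above |

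Read the other way, a 20 mg ceiling with a 50% increase covers doses up to 20/1.5 = 13.3 mg. At 18 mg it leaves room for an increase of only 20/18 - 1 = 11%.

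**If exposure is not proportional to dose.** With exposure proportional to dose^b, the equivalent is dose x 1.5^(1/b). For b from 0.8 to 1.2 the 18 mg figure runs from 29.9 to 25.2 mg-equivalent, 49% to 26% above 20 mg.

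**If up-titrated participants have lower exposure.** Let r be their exposure as a fraction of the average at the same dose. Section 2.2.2 says that it is lower; the figure that might size it is not available here. Under proportionality, 18 mg plus inhibitor gives 27r:

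| r | 18 mg + inhibitor (27r) | 13.5 mg + inhibitor (20.25r) |
|---|---|---|
| 0.6 | 16.2 | 12.15 |
| 0.8 | 21.6 | 16.2 |
| 1.0 | 27.0 | 20.25 |

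The 20 mg reference is exceeded when r > 20/27 = 0.74.

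**Return to 13.5 mg as a possible remedy.** At any r, 13.5 mg with the inhibitor gives 20.25/18 = 1.125 times the same person's exposure on 18 mg alone. It falls below that exposure only if the true inhibitor effect is under 18/13.5 - 1 = 33%. At a 25% increase, for example, 13.5 x 1.25 = 16.875, and 16.875/18 = 0.94.

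**The case against.** A reader might infer that up-titrated participants on a moderate inhibitor will be overexposed, or that the combination is unsafe. The documents support neither. Up-titration selects participants with lower estimated concentrations, and if r is 0.74 or less the 20 mg reference is not exceeded. There were no DLTs and no MTD was reached, so 20 mg is the highest dose shown here, not a toxicity limit. The Investigator's Brochure may hold more data. These points stand, and they make 35% a nominal figure. They do not repair Section 6.6.1, which does not use the lower-exposure argument and whose stated margin stops at about 13.5 mg.

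It would also go too far to say that 18 mg has no safeguards. Section 6.6.1 asks for careful monitoring, Section 6.5.3 repeats the Cycle 1 assessments, and Sections 6.5.1 and 6.5.2 reduce the dose for toxicity or high phosphate. Section 6.5 puts dose changes in consultation with the medical monitor. Table 3 schedules a concomitant-medication review at the same visit as the up-titration assessment, and Section 6.6 names the medical monitor as the contact for questions. All of these are general or act after the event. The only preventive rule touching a moderate inhibitor is the grapefruit restriction in Section 5.3.

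The Table 4 mismatch is strictly a cross-reference fault, separate from the inhibitor question, and Section 8.3.6 already requires the extra testing. It is raised because it concerns the same participants.

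Finally, an automatic return to 13.5 mg would be debatable. If the inhibitor effect is below 33%, it lowers exposure in people who were up-titrated because drug effect seemed too low.

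**Conclusion.** The concern holds in limited form. The margin in Section 6.6.1 covers 4.5 and 9 mg and, to within about 1%, 13.5 mg. It does not cover 18 mg, where the nominal figure is 27 mg-equivalent, 35% above the highest dose shown. That size rests on the protocol's 50% increase, dose proportionality and average exposure; with r below 1 it shrinks, and below 0.74 it disappears. The 18 mg dose is required only once the three conditions of Section 6.5.3 are met.

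The gap is in the justification and in the lack of a preventive rule for moderate-inhibitor medicines at that dose. It is not evidence of harm. The protocol does not say how many participants would be up-titrated and also take such a drug, and no count is claimed. No endpoint, analysis or sample size is affected.

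**What to change.** - **Section 6.6.1.** Limit the margin statement to doses up to 13.5 mg. State that at 18 mg a moderate CYP3A4 inhibitor should be replaced by a non-inhibiting alternative, or used only with medical monitor agreement on the pemigatinib dose (return to 13.5 mg being one option). Check serum phosphate about a week after the inhibitor starts.
- **Section 6.5.3.** Require the same agreement before up-titrating a participant already on a moderate inhibitor, using the concomitant-medication review already scheduled for Cycle 2 Day 1. Low phosphate despite an inhibitor suggests low drug effect, so this should be an individual decision, not a ban.
- **Table 4.** Extend the note so that up-titrated participants also have the Day 8 phosphate test in later cycles. This gives effect to Section 8.3.6.

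The cost is a few sentences of protocol text, one medical monitor contact and one phosphate test for each participant who combines 18 mg with a moderate inhibitor, and the Day 8 tests for up-titrated participants that Section 8.3.6 already implies.
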